## 11.5 Planned Interim Analyses

No interim analyses are planned.

## 11.5.1 Interim Safety Review

An interim safety review may include enrollment and demographic information, medical history, concomitant medications, physical assessments, clinical laboratory values, dosing compliance, and solicited and unsolicited AE/SAEs. Additional data may be requested by the SMC, and interim statistical reports may be generated as deemed necessary and appropriate by DMID. The SMC may receive data in aggregate and presented by treatment arm, including expected and observed rates of the expected AEs. The SMC will review grouped data in the closed session only. The SMC will meet and review this data at scheduled time points or ad hoc as needed during this trial as defined in the SMC charter. As an outcome of each review/meeting, the SMC will make a recommendation as to the advisability of proceeding with study vaccinations (as applicable), and to continue, modify, or terminate this trial.

Additionally, this trial will be monitored to determine if any of the halting rules described in Section 9.5 are met.

## 11.6 Final Analysis Plan

Participant unblinding will occur and the final CSR will be completed after the last participant's last visit is completed, the final clinical database including all long-term safety follow-up data is cleaned, monitored and locked, and all primary and secondary immunogenicity data are available. There are no planned exploratory immunogenicity endpoints. If any are added via protocol amendment, then the additional exploratory immunogenicity endpoint data not available at the time of CSR preparation may be included in an addendum to the CSR.

A formal statistical analysis plan which defines the analyses to be included in the expedited report and the final CSR will be developed, finalized, and submitted to the FDA, prior to unblinding for any analysis.

#### 11.6.1 Analysis Populations

The Safety Analysis population includes all participants who received the first dose of study vaccine.

The modified intent-to-treat (mITT) population includes all randomized participants who received the first dose of study vaccine and contributed at least one post-first study vaccination venous blood sample for immunogenicity testing for which valid results were reported. For

analyses using the mITT population, participants will be grouped based on randomized treatment arm.

The per protocol (PP) population includes all participants in the mITT with the following exclusions:

- Data from all available visits for participants found to be ineligible at baseline.
- Data from all visits for participants that did not contribute venous blood samples for immunogenicity testing.
- Data from all visits subsequent to major protocol deviations, such as:
  - Second vaccination not received
  - Second vaccination received out of window
  - Receipt of immunosuppressive therapy (e.g., corticosteroids) within 30 days before or after the first study vaccination.
  - Receipt of non-study licensed live vaccine within 30 days before or after each study vaccination.
  - o Receipt of non-study licensed, inactivated vaccine within 14 days before or after each study vaccination.
- Data from any visit that occurs substantially out of window.

For analyses using the PP population, participants will be grouped based on study vaccinations received.

#### 11.6.2 Safety Data

Summaries and analysis of safety data will be presented for the Safety Analysis Population. All summaries and analyses will be presented for all participants.

Solicited AEs will be summarized by severity after each study vaccination (through 7 days post study vaccination, Days 1 through 8 and Days 15 through 22) and as the maximum severity over all days. Additionally, solicited AEs will be analyzed by taking the most severe response over the follow-up period, dichotomizing into a binary variable (none versus mild, moderate, or severe) and using standard techniques, such as exact confidence intervals, to summarize the proportion of subjects reporting each symptom, any injection site symptom, and any systemic symptom. Summaries of solicited AEs will be presented for each study vaccination by treatment arm. The proportion of participants reporting symptoms may be compared between treatment arms using Chi-square or Fisher's exact test.

Unsolicited AEs will be coded by Medical Dictionary for Regulatory Activities (MedDRA®) for preferred term and system organ class (SOC). The numbers of SAEs, MAAEs, and AESIs

(PIMMCs) are likely to be small in this trial and will be reported by detailed listings showing the event description, MedDRA® preferred term and SOC, relevant dates (study vaccinations and AEs), severity, relatedness, and outcome for each event. Non-serious unsolicited AEs will be summarized as number and percentage of participants reporting at least one event in each MedDRA® preferred term and SOC, cross tabulated by severity and relationship to study product. Additionally, the proportion of participants and exact 95% confidence intervals of AEs in aggregate and by MedDRA® categories will be computed.

Clinical laboratory data will be summarized by severity for each visit and as the maximum over all post-study vaccination visits. Graphical presentations may include box plots.

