Because of this potential risk, individuals with a history of autoimmune disorders or active autoimmune disease (PIMMCs) will be ineligible for this trial. Additionally, because of the possibility of a delay between the vaccination and onset of symptoms indicative of a disease process of this kind, all participants will be followed for PIMMCs throughout the trial (for 12 months after the second vaccination, to approximately Day 380). PIMMCs will be captured as "Adverse Events of Special Interest" (AESI). Blood samples will be collected before vaccination from all participants for possible laboratory evaluation should suspicion of a PIMMC arise during study participation. Participants who discontinue study treatment will be encouraged to attend all subsequent clinic visits and safety follow-up contacts to facilitate this monitoring.

Local Reactogenicity. During clinical testing in which 241 participants were exposed to the combination of BioThrax + CPG 7909, the most common local reactions were mild to moderate pain, tenderness, and arm motion limitation. These reactions often resolved within 48 hours after vaccination. The most common local AEs (reported in ≥ 5% of participants in at least one of the AV7909 arm(s) from the three completed clinical trials) included injection site pain, arm movement impairment, warmth, edema/induration, erythema, hemorrhage, and pruritus.

Systemic Reactogenicity. During clinical testing to date, in completed trials in which participants were exposed to the combination of BioThrax + CPG 7909, systemic reactogenicity manifested primarily as mild to moderate fatigue, muscle ache, and headache. The most common systemic AEs (reported in  $\geq$  5% of participants in at least one of the AV7909 arm(s) from the three completed clinical trials) included fatigue, myalgia, headache, respiratory rate increased, pyrexia, pharyngolaryngeal pain, nausea, upper respiratory tract infection, and chills.

Laboratory Findings. During clinical testing to date, in completed trials in which participants were exposed to the combination of BioThrax + CPG 7909, the most common reported laboratory findings after vaccination were hypokalemia, lymphocyte count decreased, leukopenia, hypoglycemia, blood creatine phosphokinase increased, and hemoglobin decreased.

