## **5.2** Treatment Assignment Procedures

#### **5.2.1** Enrollment and Randomization Procedures

Per ICH E6 GCP, screening records will be kept at the participating VTEU site to document the reason why an individual was screened, but failed trial entry criteria. The reasons why individuals failed screening will be recorded in the Statistical and Data Coordinating Center's (SDCC) Advantage eClinicalSM (Electronic Data Capture System).

Once consented and upon entry of demographic data and confirmation of eligibility for this trial, the participant will be enrolled in the electronic data capture system. The participant will be enrolled and randomly assigned with equal allocation (1:1) to 1 of 2 treatment groups, stratified by age category (18-30 years old and 31-45 years old) and by gender.

Enrollment of participants will be done online using the enrollment module of Advantage eClinicalSM. The randomization code will be prepared by statisticians at the SDCC and included in the enrollment module for this trial. Advantage eClinicalSM will assign each participant to a treatment arm after the demographic and eligibility data have been entered into the system. A designated individual at the VTEU site will be provided with a code list for emergency unblinding purposes, which will be kept in a secure place.

Instructions for use of the enrollment module are included in the Advantage eClinicalSM User's Guide. Manual back-up procedures and instructions are provided for use in the event that the participating VTEU site temporarily loses access to the internet or the online enrollment system is unavailable.

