#### 9.3.1. Solicited Events and Symptoms

Systemic solicited adverse events were collected pre-vaccination, and systemic and local solicited adverse events were collected 30 minutes post-vaccination and then daily for 7 days after each vaccination and graded on a scale of 0 (absent), 1 (mild), 2 (moderate) and 3 (severe). Systemic events include fever, feverishness, fatigue, malaise, myalgia, arthralgia, headache, and nausea, with grading scales as defined in Table 8; the quantitative grading scale for fever is included in Table 9. Injection site events include pain, tenderness, pruritus, ecchymosis, erythema/redness, and edema/induration with grading scales as defined in Table 6. Ecchymosis, erythema/redness, and edema/induration are measured by both functional and measurement grading scales as defined in Table 7.

The number and percentage of subjects reporting at least one solicited adverse event will be summarized for each solicited adverse event, any systemic symptom, any local symptom, and any symptoms. Corresponding 95% CIs will be calculated using Clopper-Pearson methodology from a binomial distribution (SAS Proc Freq with a binomial option). Solicited events occurring post first vaccination will be presented in Table 35, post second vaccination in Table 36, and post any vaccination in Table 37. Summaries of solicited events following any vaccination will be stratified by sex in Table 38 and stratified by age category in Table 39.

For each systemic and local event, any systemic event, any local event, and any solicited event, the maximum severity over 7 days after each vaccination will be summarized for the safety population. The number and percentage of subjects reporting each event will be summarized by the maximum severity and study arm, separately for each vaccination and over all vaccinations (Table 40, Table 41 and Table 42).

The number of subjects reporting a solicited adverse event will be summarized for each day post vaccination for each vaccination and for all vaccinations combined both in tabular form (Table 43, Table 44, Table 45 and Table 46) and graphically in bar charts (Figure 15 and Figure 16). A comparison of the event rate for each study arm between vaccination 1 and vaccination 2 will be presented in Table 47.

Solicited adverse events by subject will be presented in Listing 10 and Listing 11.

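### Tolerability is to be compared between formulations, but the plan has no between-arm estimate for solicited reactions, and the one optional test it names cuts grade at none versus any, where a shift in severity can go unseen

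*Protocol*

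**What the plan says.** Tolerability is a primary objective in both documents (Protocol Table 1; SAP 3.1.1). Protocol Section 4 and SAP 4.1 say that the two formulations will be both assessed and compared on it. The outcome is the occurrence of solicited injection-site and systemic events in the week after each dose.

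Protocol 11.6.2 first keeps the grades: "Solicited AEs will be summarized by severity after each study vaccination", and as the maximum over all days. It then adds a second analysis of the worst response, "dichotomizing into a binary variable (none versus mild, moderate, or severe) and using standard techniques, such as exact confidence intervals". The only between-arm method named follows: "The proportion of participants reporting symptoms may be compared between treatment arms using Chi-square or Fisher's exact test".

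SAP 9.3.1 plans percentages with any event by arm, with Clopper-Pearson intervals (Tables 35-37). It also plans severity tables: "The number and percentage of subjects reporting each event will be summarized by the maximum severity and study arm" (Tables 40-42). It adds a breakdown by the stratification factors: "Summaries of solicited events following any vaccination will be stratified by sex in Table 38 and stratified by age category in Table 39". Table 47 cross-tabulates dose 1 against dose 2 within each arm. No table gives a difference between arms, an interval for one, or a test. SAP Section 15 does not mention that the protocol's optional comparison has been left out.

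**The concern.** The protocol describes the usual local response to this product by grade: "the most common local reactions were mild to moderate pain, tenderness, and arm motion limitation". If most recipients of both formulations have at least a mild reaction, a worse formulation would show mainly as a move from mild to moderate or severe. A cut at none versus any cannot register that move, because nearly everyone falls on the same side of it.

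Two things are at stake. If a comparison is made as the protocol describes it, a non-significant result could be read as similar tolerability when the severity profiles differ. If it is not made, which is what the SAP implies, the primary tolerability outcome is reported one arm at a time. The reader is then left to judge the difference by eye, or the cut-point is chosen after unblinding.

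**Working it through.** **Inputs.** From the documents: 20 per arm (Protocol 11.4.3), four grades from none to severe, and a chi-square or Fisher test on none versus any (Protocol 11.6.2). A two-sided 5% level is taken from the immunogenicity illustration in the same section, since none is stated for reactogenicity. Assumed: the grade distribution and the size of the shift.

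**The plan's own power figure.** There is none for this comparison. The nearest is Protocol Table 13, for immunogenicity responders at 18 per arm. Summing binomial probabilities over all outcomes that the likelihood ratio test rejects gives 79.2% to 81.1% power at its six pairs. The table's 80% reproduces, but it concerns a different outcome.

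**A limit that needs no assumed distribution.** Suppose all 20 lyophilized recipients react and k of 20 liquid recipients do not. Two-sided Fisher p = 2 × C(20,k)/C(40,k).
- k = 4: 2 × 4,845/91,390 = 0.106
- k = 5: 2 × 15,504/658,008 = 0.047

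So with four or fewer reaction-free liquid recipients, Fisher cannot show the lyophilized arm as worse, whatever the grades. The uncorrected chi-square limit is one lower:
- k = 4: 40 × 80²/(20 × 20 × 4 × 36) = 4.44, p = 0.035
- k = 3: 40 × 60²/(20 × 20 × 3 × 37) = 3.24, p = 0.072

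At k = 4 the expected reaction-free count is only 2 per arm, where that approximation is weak.

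**Power under assumed grades.** Take the liquid arm as 10/60/25/5%. A cumulative odds ratio of 3 divides the odds of being at or below each grade by 3:
- none: 0.111/3 = 0.037, or 3.6%
- mild or less: 2.333/3 = 0.778, or 43.8%
- moderate or less: 19/3 = 6.33, or 86.4%

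The lyophilized arm is then about 4/40/43/14%, and moderate-or-worse is 30% versus 56%. Fisher and chi-square power are the summed binomial probabilities of all rejected tables at 20 per arm. Wilcoxon power is simulated with a tie-corrected variance; its null rejection rate is 4.8%.

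| Liquid arm, none/mild/moderate/severe (OR 3) | Fisher, none vs any | Chi-square, none vs any | Wilcoxon on grade |
|---|---|---|---|
| 10/60/25/5% | 2% | 7% | 42-43% |
| 20/50/25/5% | 11% | 20% | 44-45% |
| 40/35/20/5% | 23% | 34% | 46% |

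With OR 5 in the first row, Fisher has 3% and Wilcoxon 74%. With 90% reacting in both arms and moderate-or-worse at 20% versus 60% (10/70/18/2% against 10/30/40/20%), Fisher has 1% and Wilcoxon 65%.

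**Away from the ceiling.** For a 20-point difference in any reaction, Fisher has 14% to 24% power; for a 40-point difference, 60% to 74%. At 50% versus 70% reacting (OR 2.33), Fisher has 16% and Wilcoxon 29%.

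**Stratification.** With four strata of five per arm, a stratified Wilcoxon (van Elteren) test moves power by about -2 to +3 points against the unstratified one, including with a moderate stratum effect.

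**What an estimate would show.** At 30% versus 56% moderate-or-worse, the difference is 26 points. The approximate 95% half-width is 1.96 × √(0.30 × 0.70/20 + 0.5625 × 0.4375/20) = 1.96 × 0.151, or about 30 points.

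**The case against.** The strongest reply is that no planned inference rests on this test. It is optional, the SAP plans no between-arm test of solicited events at all, and both documents disclaim formal hypothesis testing (Protocol 11.2; SAP 5 and 6.8). Cutting at none versus any also matches an outcome defined as occurrence. All of this stands, and it makes the point one of improvement, not of error. It does not supply the comparison that the design describes.

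A reader might go further than the documents allow in four ways.
- That severity is discarded. It is not: Tables 40-42 put the arms side by side by worst grade, per dose and over both, with within-arm intervals. Moderate-or-worse can be had by adding two rows.
- That the comparison has almost no power in general. That holds only near the ceiling, and no document gives the share of AV7909 recipients who react. The quoted description of local reactions says which were commonest, not how many people had them. Off the ceiling, 20 per arm is the main limit on any test. The odds-ratio scenarios are also a setting that suits Wilcoxon.
- That ignoring the strata is a material flaw. Randomisation is "stratified by age category (18-30 years old and 31-45 years old) and by gender", but using these strata changes power by only a few points. A gain of six points (35% to 41%) needs an assumed sex effect of OR 5, and the SAP already tabulates reactions by sex and by age.
- That the trial would declare no difference. Nothing in the plan turns a non-significant exploratory p-value into that claim.

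**Conclusion.** The point holds in limited form. The one between-arm comparison named for solicited events is blind to a grade shift when most participants react, and the SAP puts no between-arm estimate in its place. The Fisher limit of four or fewer reaction-free liquid recipients follows from the sample size alone. The power contrast (about 2% against 43% at 10% reaction-free, narrowing to 23% against 46% at 40%) rests on assumed grade distributions and a cumulative odds ratio of 3. Because severity is tabulated by arm and the test is optional, no planned conclusion is at risk. This is a cheap improvement to how a primary outcome is compared.

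**What to change.** Before unblinding, amend Protocol 11.6.2 and SAP 9.3.1 together:
- Add the lyophilized-minus-liquid difference in the percentage whose worst grade is moderate or severe, with a 95% CI (a score-type interval suits 20 per arm). Give it for any injection-site and any systemic reaction, after each dose and over both doses: 2 × 3 = 6 estimates.
- If a between-arm test is run, apply a Wilcoxon test to the ordered worst grade instead of none versus any, and label it exploratory. Stratifying by sex is optional and adds little.
- Keep none versus any as a descriptive row.
- State in SAP Section 15 what has become of the protocol's optional chi-square or Fisher comparison.

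The cost is wording and a few lines of programming on data already collected. The downside is a handful of further unadjusted exploratory results, with wide intervals (about ±30 points in the example above).

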## 11.6.3 Humoral Immunogenicity Data

Summaries and analysis of immunogenicity data will be presented for the mITT and PP populations; the PP population will be considered the primary analysis. Immune responses in terms of TNA ED50 and NF50, and anti-PA IgG by ELISA will be summarized by treatment arm at each time point. Analysis at all time points will include geometric mean titers (GMTs) and proportion of participants with seroconversion (defined as  $\geq$ 4-fold increase over baseline levels, or a  $\geq$ 4-fold increase over the LLOQ if the baseline value is <LLOQ). Additionally, the proportion of subjects in each study group with putative seroprotection (defined as NF50 $\geq$ 0.56) will be assessed at each time point. All summaries will include the corresponding 95% confidence interval. No exploratory immunologic outcomes are anticipated.

## 11.6.4 Exploratory Immunogenicity Data

None.

#### 11.6.5 Missing Values and Outliers

All attempts will be made to collect all data per protocol. As missing data are expected to be minimal, no imputation will be performed for missing values. Any data point that appears to be erroneous or inexplicable based on clinical judgment will be investigated as a possible outlier. If data points are identified as outliers, sensitivity analyses will be performed to examine the impact of including or excluding the outliers. Any substantive differences in these analyses will be reported.

## 12 DATA COLLECTION FORMS AND ACCESS TO SOURCE DATA/DOCUMENTS

The participating VTEU site will maintain appropriate medical and research records for this clinical trial, in compliance with ICH E6 GCP Section 4.9 and regulatory and institutional requirements for the protection of confidentiality of participants. The participating VTEU site will permit the study monitor or other authorized representatives of DMID as well as governmental regulatory agencies, such as the FDA, to examine (and when required by applicable law, to copy) clinical trial records for the purposes of quality assurance reviews, audits, monitoring and evaluation of the study safety and progress. These representatives will be permitted access to all source data, which include, but are not limited to, hospital records, clinical and office charts, laboratory notes, memoranda, evaluation checklists, pharmacy dispensing records, recorded data from automated instruments, copies or transcriptions certified after verification as being accurate and complete, microfiches, photographic negatives, microfilm or magnetic media, x-rays, and participant files, and records kept at the pharmacy, at the laboratories and medico-technical departments involved in this clinical trial. Source data are all information, original records of clinical findings, observations, or other activities in a clinical trial necessary for the reconstruction and evaluation of the clinical trial.

Interview of participants is sufficient for obtaining medical history. Solicitation of medical records from the participant's primary care provider is not required.

The study uses direct data entry for the participating clinic site and a web-based electronic Memory Aid (eMemory Aid) for participants. All eCRFs serve as the source documents. Participants will be trained to use a database to complete a web based "eMemory Aid" and are expected to enter information in the eMemory Aid each day. Participants using the eMemory Aid will also be provided a paper memory aid for their use in the event they are unable to access the web-based system. The participants will be asked to enter the information from the paper memory aid into the eMemory Aid once they are able to access the web-based system.

Participants will record temperature, local and systemic symptoms, and if any new medications were used following vaccination or changes to previously reported medications daily for 8 days after any vaccination (Days 1 through 8 and Days 15 through 22).

Participants will be instructed to contact the clinic staff immediately if they experience significant symptoms at any time during the study, for prompt follow-up in real time. The study clinic will be alerted in real time of any potential solicited events of Grade 3 severity entered in the eMemory Aid. An email alert will be sent to the clinic site and the Emmes study team. Within one business day of site awareness, the site must attempt to follow up with the participant

on the severe solicited event and send an email to Emmes confirming attempted follow up with the participant. Instructions for completing the eMemory Aid are provided in the MOP and in a separate eMemory Aid instructions document that will be provided to the participants at each vaccination. The site staff must review the eMemory Aid information and interview the participant at the next scheduled visit. The participant-entered data will be included in the clinical database on the Solicited Events eCRF and will be available for review by the clinician during the clinical interview. All participant-entered data are to undergo clinical review.

Site staff who are delegated the responsibility by the study PI will be the data originators for clinical data entered directly into the eCRF in Advantage eClinical that will be used for the study endpoints. The central laboratory will be the data originator for laboratory data reported by an automated reporting system. A list of all authorized data originators, including site staff, will be included on the Study Personnel/Signature Responsibility List.

